Data Analysis Plan. SPM12 ⁵⁵ will be used for fMRI statistical analyses. EPI time series' preprocessing will include: (1) realignment for motion correction, (2) slice timing correction, (3) co-registration of EPI with anatomical data, (4) spatial normalization to MNI anatomical, and (5) spatial smoothing. Head motion outliers in EPI time series will be corrected using the Artifact Detection Tools with a scan-to-scan movement threshold of 0.2 mm and a scan-to-scan global signal change of 3 SD ⁵⁶. Activity. For each subject, BOLD activity contrast signal variance will be modeled with regressors using a General Linear Model (GLM) to generate 1st level contrasts (NF vs. CB and NF vs. Rest) for the ESF-NF task similar to procedures followed by Young et al. ³². [name] will lead activity analyses. Connectivity. Time series in dACC or right-amygdala for the ESOM and ER tasks will be used to yield general psychophysiological interaction (gPPI) contrast variables ⁵⁷. The gPPI variables represent FC differences for 'self' vs. 'other' faces recognition or 'regulation' vs. 'passive' viewing. The processing pipeline configuration will be available online. The research staff and a software programmer will generate automatic pre-processing scripts using pilot adult data to yield 1st level images for both activity, connectivity, and structural data to ensure rapid quality control and data access. General PPI analyses yield information flow between neural nodes without direction of exchange. Competing models of affect valuation versus affect modulation/suppression assume 'bottom-up' influence from amygdala on mPFC or 'top-down' influence from the mPFC and dACC on the amygdala, respectively⁵⁸. Dynamic causal modeling (DCM)⁵⁹⁻⁶¹ will follow up gPPI analyses to test bottom-up vs. top-down models of information flow between target neural hubs. DCM will also test FC patterns during NF training but increase target activity during NF is the key target for our Milestone 1. [name] will conduct FC analyses and determine how functional neuro-architecture of affect regulation and self-processing changes after NF training. Defining ROIs. In line with our focus on amygdala, dACC, and their connectivity with mPFC, we will target the dACC (MNI: x=-8, y=30, z=30), the highest loci of activity within the ACC in our pilot results and the right amygdala (MNI x=28 y=0 z=-19), the loci of our amygdala-ACC FC results in attempting participants ⁴¹. ROIs of activity (5 mm) centered in those coordinates during NF, and their FC to mPFC (polar aspects of BA10-9) during ER and ESOM tasks are the target ROIs. The unrelated locus is the left horizontal segment of the intraparietal sulcus (MNI x=-42 y=-48 z=48). This region is not involved in emotion regulation or self-processing and has been used before as a locus of Unrelated comparison NF ^{32,34-36}. Finally, our decision of using specific coordinates, instead of localizing ROIs with a task that elicits dACC or amygdala activity, is supported using pre-determined coordinates for NF in research that yielded ROI up-regulation and symptoms improvement ^{32,34-36}. Accordingly, we have selected coordinates based on our published and pilot work. Puberty ⁵¹, illness or depression (BDI) severity, treatment indexes, substance use, IQ, handedness, or any variable differing between key groups will be covariates in all analyses.

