
Power Analysis: Power and R61 Milestones. With N=40 (20 per NF's loci), the R61 phase yields 80% power to detect an effect size of $d=0.49$ for one of the loci. Our data yielded statistically significant effect sizes of dAmygdala=0.37 and ddACC=0.324 in activity increases during a short version of the proposed ESF-NF task. Longer NF duration yield effect sizes as large as $d= 1.2$ as shown by Young et al. ^{32,34-36}. Since we focus on target circuitry identified by prior studies, we will employ region of interest (ROI) for connectivity and activity analyses in the R61 phase.

Statistical Analysis: Milestone (1-2) tests: Neural targets' activity (dACC or Amygdala) during NF will be tested using 1st-level NF vs. CB similar to Zotev et al. ³⁶ and NF vs. Rest, similar to Young et al. ^{32,34-36} in single-sample t-tests (p-corrected, 0.01 using the AFNI program 3dClustSim voxel-level threshold of $p<0.001$) to identify regional effects controlling for key covariates noted in C3.2 for the ROIs and to estimate effect sizes during the ESF-NF task. Tests proposed for the ESF-NF task will be also conducted with the baseline and transfer runs to establish baseline (pre-NF) and post-treatment engagement of the neural targets. Neural targets' connectivity after NF. NF training effects in self-processing and affect regulation neural circuits during the ESOM and ER tasks, will

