be performed on 1st-level gPPI contrast images⁶² representing FC estimates for ‘self’ vs. ‘other’ faces recognition and for ‘regulate’ vs. ‘passive’ viewing conditions (with similar thresholds as above). Right-amygdala or dACC to mPFC FC will be tested with 1st level gPPI maps in mixed-effects analysis-of-variance (ANOVA) with time as within-group effects (Pre- and Post-NF training) to model FC parameters and compute effect sizes⁵⁷. In a follow-up DCM analyses we will test for direction of information flow between hubs identified with gPPI analyses. Models for all plausible configurations of causal information exchange between two neural nodes (amygdala or dACC and mPFC) will be defined. The ESOM and ER task conditions are assumed to drive causal information flow. Links with psychological targets: Amygdala and dACC to mPFC FC will be extracted and correlated with changes in psychological targets, i.e., emotion regulation and self-processing behavior in the ETB⁴⁰ and IAT^{38,39} before vs. after NF training. We will also test correlations with self-reported change (DERS, SPPA, RD) in those constructs²³⁻²⁵.

R33 Aim 1: Confirm target engagement in the NF versus the Unrelated-NF group.

H1.1: Right amygdala or dACC activity will be higher for active versus unrelated-NF. A Bayesian ANOVA model will be fit for each ROI, where the primary predictor for each model is the indicator for the NF group, which will quantify the difference in activity parameters between the NF and Unrelated-NF groups.

H1.2: Right amygdala or dACC – mPFC FC will be higher during self-processing and affect regulation tasks following active NF compared to Unrelated-NF training sessions. A Bayesian analysis-of-covariance (ANCOVA) will model how each of the FC parameters relate to each of the affect dysregulation and self-processing behavioral scores. The predictors will be the NF indicator terms, which will quantify how each of these scores are affected by NF, the main effect of the neural target, and the interaction term between main effect and NF indicator. This interaction term will measure the difference in the association between the neural targets and the behavioral scores between the NF and Unrelated-NF groups.

R33 Aim 2: Test the relationship between neuropsychological targets’ engagement and behavioral changes.

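### The R61 power figure (80% at d = 0.49) has no alpha, sidedness or test, and should not be read as power for the planned 0.01 tests or as the chance of meeting Milestone 1

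*Combined protocol and SAP*

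**What the plan says.** Section 18, Power Analysis, gives N = 40 with 20 per locus and states that "the R61 phase yields 80% power to detect an effect size of $d=0.49$ for one of the loci". The sentence gives no alpha, sidedness or test, and does not say whether one of the loci means a locus named in advance or either of the two. The same paragraph gives pilot results: "Our data yielded statistically significant effect sizes of dAmygdala=0.37 and ddACC=0.324 in activity increases", from a short version of the task. It adds "Longer NF duration yield effect sizes as large as" d = 1.2.

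The Statistical Analysis paragraph that follows, headed as the tests for Milestones 1 and 2, names single-sample t-tests for activity at "p-corrected, 0.01 using the AFNI program 3dClustSim voxel-level threshold" p < 0.001. Their stated purpose is "to identify regional effects controlling for key covariates noted in C3.2 for the ROIs and to estimate effect sizes during the ESF-NF task". The connectivity (FC) tests are run "with similar thresholds as above".

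Section 1 sets Milestone 1 as a condition for moving to R33: the trained locus must show higher activity during neurofeedback, and higher FC with mPFC in the ESOM or ER task, with d of at least 0.4. It names no p-value. Section 18 also says that "increase target activity during NF is the key target for our Milestone 1", and defines the regions as "ROIs of activity (5 mm) centered in those coordinates during NF, and their FC to mPFC".

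**The concern.** This is the only power figure given for R61, and its paragraph is titled as covering the R61 milestones. A reader will therefore take it either as power for the tests in the next paragraph or as reassurance about Milestone 1. It is not shown to be either. The tests use a stricter threshold than any that recovers 80%, and the milestone is a cut-off on the observed effect size, not a rejection of a null hypothesis.

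Milestone 1 is one of two conditions for starting R33, in which 70 participants are to be randomized. Those who judge whether R61 is large enough for that decision have no figure that describes it. The meaning of one of the loci also matters: at two-sided 0.05, the two readings differ by about 25 percentage points.

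**Working it through.** **Inputs.** From Section 18: n = 20 per locus, d = 0.49, power 80%, single-sample t-test, corrected p 0.01, pilot d 0.37 (amygdala) and 0.324 (dACC), upper figure 1.2. From Section 1: cut-off d ≥ 0.4. Assumed here: one mean ROI value per participant, one contrast, no covariates, independent loci.

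**Formulas.** Per-locus power p comes from the noncentral t distribution with df = 19 and noncentrality d√n = 0.49 × √20 = 2.191. Power for at least one of two independent loci is 1 − (1 − p)².

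**Step 1: reproduce the plan's figure.** At two-sided 0.05 the critical t is 2.093 and p = 0.548. For at least one locus, 1 − (1 − 0.548)² = 0.795, and the d detectable with 80% power is 0.493. This matches the plan. One named locus at one-sided 0.10 also gives 80.6%.

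**Step 2: find which alpha gives exactly 80% at d = 0.49.**

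| Reading | Two-sided | One-sided |
|---|---|---|
| One named locus, n = 20 | 0.193 | 0.097 |
| At least one of two loci | 0.051 | 0.026 |
| All 40 pooled | 0.030 | 0.015 |

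All are looser than 0.01.

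**Step 3: power at 0.01, for an ROI-mean t-test.** This is not the cluster-corrected map test, whose power the documents do not allow anyone to compute.

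| Alpha | Per locus | At least one |
|---|---|---|
| 0.01 two-sided (critical t 2.861) | 0.283 | 1 − 0.717² = 0.486 |
| 0.01 one-sided (critical t 2.539) | 0.386 | 1 − 0.614² = 0.623 |

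**Step 4: chance that observed activity meets d ≥ 0.4.** With n = 20, this is the probability that t is at least 0.4 × √20 = 1.789.

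| True d | Per-locus chance |
|---|---|
| 0.49 | 0.659 |
| 0.37 (amygdala pilot) | 0.458 |
| 0.324 (dACC pilot) | 0.381 |
| 1.2 | 0.9997 |

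For at least one locus the chance is 1 − (1 − 0.659)² = 0.884 at a true d of 0.49 in both, and 1 − (1 − 0.458)(1 − 0.381) = 0.664 at the two pilot effects. Milestone 1 also needs the FC effect, so for a single activity contrast these are upper bounds on passing.

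**Step 5: the true d needed with 20 per locus.**

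| Target | Named locus | At least one |
|---|---|---|
| 80% power, two-sided 0.05 | 0.66 | 0.49 |
| 80% power, two-sided 0.01 | 0.84 | 0.66 |
| 80% power, one-sided 0.01 | 0.76 | 0.59 |
| 80% chance of observed d ≥ 0.4 (activity only) | 0.59 | 0.43 |

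**Step 6: sample size.** Section 11.1 gives a minimum of 60 participants and Sections 18 and 29.1 give 40, yet Sections 11.1 and 29.1 both arrive at 20 data sets per target. If 60 meant 30 per locus (an assumption that the text does not support), ROI-mean power at d = 0.49 and 0.01 would be 48% two-sided or 59% one-sided per locus. For at least one locus it would be 1 − 0.518² = 73% or 1 − 0.408² = 83%.

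**The case against.** The strongest reply is that the figure is correct. It matches at-least-one-of-two power at the conventional two-sided 0.05 almost exactly, which is probably how it was derived. This stands: a reader might infer an arithmetic error, and the documents do not support that. What is missing is the statement of that reading.

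Second, the 0.01 belongs to a cluster-corrected map, so the 28% to 62% figures are not power for any test as written. This also stands. They show only what an ROI-mean test would have at that alpha; no one can say from the documents that the planned map tests fall short of 80%.

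Third, a reader might infer that the 0.01 tests gate the decision, so that the 0.4 cut-off never matters and effects somewhat above it would be in dispute. Section 1 states no significance condition. Section 18 puts the tests under a milestone heading but does not say that they decide passage, and a significant cluster filling part of an ROI could coexist with an ROI-mean d below 0.4. That inference is not supported; the question only needs a plain answer.

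Fourth, the plan already commits R61 to ROI analyses and to extracting FC values. This is true, and it makes the remedy cheaper. The plan still does not say that the milestone d is an unthresholded ROI mean.

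Fifth, longer training may give much larger effects. At d = 1.2 the activity part passes more than 99% of the time, but the plan presents 1.2 as an upper figure, and both of its own pilot effects lie below 0.4.

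**Conclusion.** The point holds as a problem of specification and interpretation. The 80% is reproducible at an alpha that the R61 plan never states, and only if one of the loci means at least one of two; a named locus would have 55% at two-sided 0.05. It should not be presented as power for the planned tests, because every t-test reading examined needs a looser alpha than 0.01 to reach 80%.

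It is also not the probability of meeting Milestone 1. For activity alone, that is 66% per locus at the plan's own d of 0.49, 46% and 38% at its pilot effects, and close to certain at 1.2.

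These sizes rest on the assumptions listed with the inputs. Covariates, which the plan does intend, cost degrees of freedom but may reduce residual variance. If either activity contrast (against counting backward or against rest) could satisfy the milestone, the chance of passing would rise. It is worth fixing before milestone data are seen.

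**What to change.** 1. Reconcile the R61 sample size across Sections 11.1, 18 and 29.1.
2. Define the Milestone 1 activity and FC effect sizes as computed from one unthresholded mean value per participant in the ROIs already set out in Section 18, with confidence intervals. Keep the 3dClustSim maps as supporting output.
3. State that Milestone 1 is decided on d ≥ 0.4, as Section 1 says, or else that significance is also required, with one alpha and sidedness.
4. Restate the R61 power with its test, alpha, sidedness and the meaning of one of the loci, and add the pass probability for the chosen rule over a range of true effects that includes the pilot values. The last table of the working gives the entries for 20 per locus.

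The cost is wording plus an ROI-mean extraction from regions already defined. The drawback is that the restated figure may look less favourable, especially under a 0.01 or named-locus rule.

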ESOM_NF, Emotional-Self-Other Morph Neurofeedback
ESOM-Pre, ESOM task presented before ESOM_NF task
ESOM-Post, ESOM task presented after ESOM_NF task
ER; Emotion Regulation Task;
FC; functional connectivity
IAT, Implicit Association Test;
IMM; Independent Medical Monitor;
MDD: Major Depressive Disorder;
mPFC, Medial Prefrontal Cortex;
mPFC FC; medial prefrontal cortex functional connectivity
NF, Neurofeedback;
QR; Quick Response Code
ROI, region of interest;
PTSD: Post Traumatic Stress Disorder;
Personal Health Information: PHI
UMN: University of Minnesota

1. Objectives

R61 Phase Specific Aims: Given the modest efficacy of current evidence-based treatments ¹⁻⁷, novel, personalized interventions for adolescent suicide behaviors are needed. Repeated suicide attempts are predicted by abnormal self-processing and affect dysregulation ^{4,8-13}. Abnormal self-processing is neglect of positive self-relevant information and excessive focus on negative information. Self-processing (e.g., self-face recognition) is enabled by the dorsal anterior cingulate cortex (**dACC**) ¹⁴⁻¹⁶ and medial prefrontal cortex (**mPFC**) ⁴⁰⁻⁴. Those neural hubs enable awareness of salient stimuli ¹⁷ and affect regulation, which is modulation of emotions borne by neural hubs such as the **amygdala** ¹⁸. Adolescence is a neuroplastic period for the circuits of affect regulation and self-processing ^{19,20}. It is unknown whether engaging those circuits using novel interventions could reduce suicide risks, e.g., suicide ideation. To begin to address this knowledge gap, in the R61 phase we will test the efficacy of neurofeedback training to engage the neurocircuitry of self-processing and emotion regulation (dACC, mPFC and amygdala) in 1st time suicide attempting Participants.

To establish target engagement, **in the R61 phase**, participants will be trained to increase the activity of one of two competing neural hubs ($N_{dACC}=20$ or $N_{Right-Amygdala}=20$). We will identify which circuits are better engaged during and after NF in time suicide attempting participants (11-18 years) with current suicide ideation as well as 17 – 45 y.o participants with symptoms of borderline personality disorder. Behavior and circuits of affect regulation and self-processing will be sampled before and after two NF training sessions.

The **R61 milestones for proceeding to the R33 phase are:**

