Description. Neurofeedback training is a modality of biofeedback. During neurofeedback training, a person that is inside the scanner can see the changing levels of activity of a selected brain region. Because regional neural activity is visually displayed to a person in the scanner, this enables voluntary modulation of neural activity in regions of interest, which can trigger corrective neuroplastic processes. We will deliver neurofeedback training using the **Emotional Self-Face Neurofeedback, ESF-NF paradigm**^{30,31} comprised by four ~7.33 min NF training runs preceded by a 5 min baseline (ESF no NF), a 5 min practice run, and followed by a 5 min transfer run (ESF no NF)³². Training entails NF blocks paired to a self-happy face visual that signals the start of NF. There will be two control conditions to distract participants from contemplating positive memories and dampen affect regulation and self-processing networks. During one control condition participants will count backwards from 100 cued by an unfamiliar happy teen face with no NF (count backward = **CB**). During other control condition participants are presented with the cue "Rest" and are asked to relax and look at the screen (**Rest**). During **NF**, participants will attempt to increase neural activity displayed via a colored bar shifting up or down depending on values provided by MURFI2 software³³. Green = Activity > baseline and red = Activity < baseline. We may adapt the feedback procedures to be more like a game, but the current description still conveys the visual feedback modality. The active NF loci will be the right amygdala or the dorsal ACC in the R61 phase. The active NF loci during the R33 phase will be the loci of higher engagement that best elicits functional improvements in the R61 phase. As in prior NF trials³⁴⁻³⁶, participants select positive autobiographical memories that they recall during NF training. **[name]** has administered a short version of the proposed task to 53 Participants^{30,31}. ROIs for the dACC, right amygdala or an unrelated site (e.g., the left intraparietal sulcus) will be localized from coordinates mapped to each participant's structural image. **[name]** has used this software and protocol with healthy and depressed participants^{30,31}. The scanning room and specifically the scanner coils already include devices to present stimuli. It is part of the hardware. We may monitor heart rate and breathing using devices that are superficially attached to the participant's torso. These devices are also often used as part of scanning procedures of human participants.

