
- 4.1 Drug/Device Handling: NA
- 4.2 Biosafety: NA
- 4.3 Stem Cells: NA
- 4.4 Fetal Tissue: NA

5. Procedures Involved

Study Design: After securing a permission to contact from participants or parents, study personnel will screen suitability (See **Phone Script**) with parents or legal representatives over the phone before scheduling the first session. Participants will be assessed in person ~2 weeks before and after NF training (Day 1: first session) and ~1 month after the last NF training. The first session visit can occur at the department of psychiatry, at the inpatient unit where the participant might still be interned, or in the same building where the patient unit is at (with permission of the leadership in the inpatient unit and provided that a secure confidential room is available).

Two to three weeks can pass between each visit. Responses from parents and clinicians might also be used for preliminary screening of participants and their families over the phone, to establish eligibility for in-person assessments. **Table 1** provides the sequence of key events. **To confirm inclusion and enable brain-behavior analyses, disorders will be established by clinicians administering the new computerized KSADS-COMP or the K-SADS-PL²⁶ interview version lead by a trained staff member.** The BDI²⁷ and CTQ²⁸ will yield additional dimensional depression and PTSD indexes. The C-SSRS⁹⁸ and SIQ²⁹ will confirm suicide ideation and attempts at baseline. The DERS²³, RD¹²⁰ and the SPPA^{24,25} will provide self-report measures of affect dysregulation and abnormal self-processing. Participants will also complete the IAT^{38,39} a behavioral task of abnormal self-processing and the Emotional Testing Battery (ETB), which measures affect regulation and self-processing⁴⁰ outside the scanner. After concluding the 1-month follow-up participants that accept remaining in touch with the experimenters may be called for

another follow-up brief phone interview and/or to be invited to other studies. This optional follow-up involves administering a few previously approved questionnaires that will measure depressed mood, feelings, suicidal thoughts and/or suicidal feelings since they last participated. **Before and after the NF training participants will complete the following tasks or alternative tasks that measure the similar constructs of affect regulation and self-processing. The following tasks are exemplars of what the participant will experience.**

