Visit 1: Baseline	Visit 2: Scan day 1	Visit 3: Scan day 2	Visit 4: Post-NF	Visit 5: Approximately 1 Month later after Visit 4.	Additional visits as needed to complete pending tasks
KSADS. Children Depression Rating Scale-Revised (CDRS). Difficulty with Emotion Regulation Scale (DERS) ²³ . Self-Perception Profile for Participants (SPPA) ^{24,25} . Responses to Depression (RD) ⁴⁸ : rumination.	SIQ, BDI, DERS, SPPA, RD Medication, psychotherapy. Review 5 happy memories.	SIQ, BDI, DERS, SPPA, RD Review 5 happy memories.	SIQ, BDI, DERS, SPPA, RD.	SIQ, BDI, DERS, SPPA, RD Online	Anything pending
Columbia-Suicide Severity Rating Scale, C-SSRS, ⁴⁹ . Suicide Ideation Questionnaire, SIQ ²⁹ .	ESOM: 14 min ER: 13 min	NF Training: ESF_NF ~ 44.32 min	C-SSRS, CDRS	KSADS-COMP and C-SSRS	Anything pending
Beck Depression Inventory, BDI ²⁷ . Child Trauma Questionnaire, CTQ ²⁸	NF Training: ESF_NF~ 44.32 min	ESOM: 14 min ER: 13 min	IAT and ETB		Anything pending
Wechsler Abbreviated Scale for Intelligence, WASI ⁵⁰ . Edinburgh handedness inventory. Write/ discuss 5 happy memories.	30 min break	30 min break	Medication, psychotherapy	Medication and psychotherapy	Anything pending
Medication, psychotherapy, demographics, and puberty stage⁵¹.					Anything pending
Implicit Association Test (IAT): Abnormal Self-Processing Behavior ^{38,39} . Emotional Testing Battery (ETB): Affect and self-processing ⁴⁰ , or another similar test. Can be administered also before scanning on scan day 1 or after scanning on scan day 2.	Ease of recall rating. SIQ, BDI, DERS, SPPA, RD.	Medication, psychotherapy. Ease of recall rating. SIQ, BDI, DERS, SPPA, RD.		IAT and ETB	Anything pending

- Items from the KSADS, C-SSRS and Medication and psychotherapy forms will be shared with the IMM to confirm inclusion vs. exclusion of participants.

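### R33 H1.1 does not pre-specify adjustment for each participant's own pre-feedback ROI activity, although the first NF session already measures it

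*Combined protocol and SAP*

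**What the plan says.** **Session structure.** Section 4 describes the ESF-NF paradigm as "comprised by four ~7.33 min NF training runs preceded by a 5 min baseline (ESF no NF), a 5 min practice run", then "followed by a 5 min transfer run (ESF no NF"). Table 1 in Section 5 lists the paradigm on both scan days, the second as "NF Training: ESF_NF ~ 44.32 min". Section 1 confirms that behaviour and circuits "will be sampled before and after two NF training sessions".

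**Use of the no-feedback runs.** Under the Milestone (1-2) tests in Section 18, the tests proposed for the ESF-NF task, NF vs. count-backward (CB) and NF vs. Rest, "will be also conducted with the baseline and transfer runs to establish baseline (pre-NF) and post-treatment engagement of the neural targets". The sentence does not say which session's runs are meant.

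**R33 activity model.** H1.1 in Section 18 reads: "A Bayesian ANOVA model will be fit for each ROI, where the primary predictor for each model is the indicator for the NF group". No baseline-run term is named.

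**Routes by which one could enter.** The Data Analysis Plan in Section 18 names puberty, severity, treatment, substance use, IQ and handedness as covariates, and adds any variable on which the key groups differ. The model-selection paragraph of Section 18 allows covariates to be added to each starting model where they improve fit. The variables on which Section 1 hopes to match the R33 arms do not include ROI activity.

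**The concern.** People are likely to differ in how strongly they activate the amygdala or dACC in this task before they have seen any feedback. In a two-arm comparison of activity during NF, that difference is noise. Some of it can be removed with a measurement the trial already takes. H1.1 leaves it in unless a data-driven step picks it up. Adjusting because the arms turned out to differ, or because a search favoured the term, makes the final H1.1 model depend on the results. It also leaves the analyst a choice that a fixed covariate would close.

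Two things are at stake. One is power in a comparison with 35 per arm. The other is the reading of an H1.1 result if the arms happen to start at different levels. A smaller matter goes with these: Section 18 has two baseline runs and two transfer runs to choose from and does not say which pair defines engagement before and after treatment.

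**Working it through.** **1. Is there a no-feedback baseline run in each session?** Run lengths are from Section 4 and session length is from Table 1.

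- With the baseline run: 4 × 7.33 + 5 (baseline) + 5 (practice) + 5 (transfer) = 44.32 min.
- Without it: 4 × 7.33 + 10 = 39.32 min.

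Table 1 gives about 44.32 min on both scan days, so its figure is reproduced and a baseline run is scheduled in both sessions. The first-session run comes before all feedback. The second-session run follows a complete NF session, and "Two to three weeks can pass between each visit". In the same way, the first-session transfer run falls mid-treatment and only the last transfer run is post-treatment.

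**2. Inputs for H1.1.**

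- n = 35 per arm: 70 randomised 1:1 (Section 1).
- d = 0.4: the Milestone 1 threshold (Section 1), used here as an illustrative between-arm effect. d = 0.49 is the effect in the R61 power statement (Section 18).
- Two-sided alpha 0.05: assumed, since H1.1 is Bayesian and states no error rate.
- r, the correlation of first-session baseline-run activity with NF-run activity: not in the documents; 0.3 to 0.7 is assumed.

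**3. Formulas (normal approximation, outcome SD = 1).**

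- Unadjusted SE = √(2/35) = 0.239.
- Adjusted SE = 0.239 × √(1 − r²).
- Power = Φ(d/SE − 1.96).
- Detectable d at 80% power = (1.96 + 0.84) × SE.

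For example, unadjusted at d = 0.4: 0.4/0.239 − 1.96 = −0.29, so power is 38.7%. At r = 0.5: SE = 0.239 × 0.866 = 0.207, 0.4/0.207 − 1.96 = −0.03, so power is 48.9%.

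| H1.1 model | Residual variance removed (r²) | Power, d=0.4 | Power, d=0.49 | Detectable d, 80% |
|---|---|---|---|---|
| No baseline term | 0% | 38.7% | 53.6% | 0.670 |
| Adjusted, r=0.3 | 9% | 41.8% | 57.5% | 0.639 |
| Adjusted, r=0.5 | 25% | 48.9% | 65.8% | 0.580 |
| Adjusted, r=0.7 | 49% | 64.9% | 81.9% | 0.478 |

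An unadjusted analysis would need 35/(1 − r²) per arm for the same precision: 39, 47 or 69.

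**4. Chance imbalance.** The between-arm difference in baseline activity also has SE 0.239 SD, so it exceeds 0.40 SD in about 9% of trials. The shift in the outcome is r times the imbalance. At 0.40 SD that is 0.12, 0.20 or 0.28 SD for r = 0.3, 0.5 or 0.7.

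**The case against.** The strongest reply is that H1.1 is a randomised comparison. Chance imbalance is already part of the uncertainty of an unadjusted estimate, so leaving the covariate out does not bias it. That stands, and it limits the point to efficiency and to conditional imbalance.

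A second reply is that H1.1 names a primary predictor, not the only one, and Section 18 leaves two ways to add baseline activity. That also stands, so it would be wrong to say the plan shuts the variable out. But both routes open only after the data are seen, which is the reason to fix the term in advance.

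A third reply is that the gain depends on an unknown r. One 5 min run may be a noisy predictor of activity over 4 × 7.33 = 29.32 min of training per session. At r = 0.3 power rises by only about 3 percentage points. This is fair, and the lower end of the range may be the realistic one.

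A reader might also infer more than the documents support:

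- *That the activity measure has no clean baseline.* It has one. The first-session baseline run precedes all feedback and falls within the Section 18 tests. Only its label is missing.
- *That the training effect is diluted because the second-session baseline run is counted as pre-NF.* Nowhere does the plan average the two baseline runs or subtract a baseline run from NF or transfer activity. The sentence on these runs adds further tests of the same contrasts.
- *That the R61 go/no-go decision is affected.* The Milestone 1 activity criterion concerns activity during ESF-NF, tested against control blocks of the same task, not change from the baseline run.

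**Conclusion.** The point holds as a matter of efficiency and pre-specification. H1.1 leaves adjustment for pre-feedback ROI activity to data-dependent steps although the measurement is already collected. At 35 per arm and d = 0.4, fixing the covariate in advance raises power from about 39% to 42%, 49% or 65% at r = 0.3, 0.5 or 0.7. It also removes the expected effect of a chance difference in starting level.

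These figures rest on a frequentist approximation to a Bayesian model, an assumed two-sided 0.05, an assumed range for r, and an effect size borrowed from the R61 milestone. Informative priors would change the absolute power. The proportional reduction in residual variance, r², is a property of the data and does not depend on the error rate.

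The unadjusted H1.1 comparison remains valid. The unnamed sessions in Section 18 are missing detail, not an error in the analysis.

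**What to change.** 1. **Section 18, H1.1.** Add as a fixed covariate the contrast from the baseline run of the first NF session, for the same ROI and the same comparison (NF vs. CB or NF vs. Rest) as the outcome. Use the target ROI in both arms. Keep this term outside the model search.
2. **Fallback.** State in advance what is done when that run is unusable, for example through motion, so that such participants are not dropped by default.
3. **Section 18, Milestone (1-2) tests.** Define pre-treatment engagement as the baseline run of the first NF session and post-treatment engagement as the transfer run of the last. Report the second-session baseline run as a retention measure and the first-session transfer run as a mid-treatment measure. Define these by session, not visit number, because the note to Table 1 lets the order and day of procedures change.

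The cost is some plan wording, one model term and one missing-data rule. No scan, visit or participant is added.
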